Summary statistics (for Screening value, Baseline value, observed values, and observed changes from Baseline) at scheduled visits will be provided for each treatment group. The summary will include the number of observations, mean, SD, standard error (SE), minimum, median, and maximum. Graphical presentations will also be used to examine trends over time using mean values ( $\pm$ SE) and mean changes from Baseline ( $\pm$ SE) at each of the scheduled visits using OC.

A sensitivity analysis will be conducted with the 52-week treatment completers (ie, all patients who complete the 52-week Treatment Period and do not start rescue therapy) using the Week 52 values and the same ANCOVA model described above.

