1 OVERVIEW AND INVESTIGATIONAL PLAN

1.1 STUDY DESIGN AND RANDOMIZATION

This study is a Phase 3 randomized, double-blind, double-dummy, active- and placebo-controlled, parallel-group, multicenter study that is anticipated to enroll approximately 930 patients.

The study will consist of a Screening Period comprised of an up to 2 weeks Screening Phase and a 2-week single-blind placebo Run-in Phase, a 52-week double-blind and double-dummy Treatment Period, and a 2-week post-treatment Follow-up Period (patients who prematurely discontinue the study treatment are expected to continue in the study).

In order to qualify for randomization, patients must demonstrate compliance during the Run-in Phase based upon tablet and capsule count ($\geq 80\%$) and as assessed at the discretion of the Investigator. Eligible patients will be randomized centrally by an Interactive Response Technology (IRT) using a permuted-block randomization schedule with a fixed block size. Randomization will be stratified by hemoglobin A1c (HbA1c) at Screening ($\leq 8.5\%$, $> 8.5\%$) and systolic blood pressure (SBP) at the screening visit (< 130 mmHg, ≥ 130 mmHg).

Following randomization, patients will be treated in a double-blind and double-dummy manner for 52 weeks. A total of 930 patients ≥ 18 years of age will be randomly assigned at a 2:1:2:1 ratio to the following four treatment groups on top of open-label metformin:

- Sotagliflozin 400 mg group: sotagliflozin 400 mg, given as two 200 mg tablets, and two glimepiride-matching placebo capsules, taken orally once daily before the first meal of the day (N = 310 patients).
- Sotagliflozin 200 mg group: sotagliflozin 200 mg, given as one 200 mg tablet and one sotagliflozin-matching placebo tablet, and two glimepiride-matching placebo capsules, taken orally once daily before the first meal of the day (N = 155 patients).
- Glimepiride group: two sotagliflozin-matching placebo tablets, and combination of two glimepiride (or matching placebo) capsules with adequate dose strengths per dose titration (titrated up to 6 mg), taken orally once daily before the first meal of the day (N = 310 patients).
- Placebo group: two sotagliflozin-matching placebo tablets and two glimepiride-matching placebo capsules, taken orally once daily before the first meal of the day (N = 155 patients).

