1.3 DETERMINATION OF SAMPLE SIZE

The sample size/power calculations were performed based on the primary endpoint of change of HbA1c from Baseline to Week 52 in the intent-to-treat (ITT) population. Assuming a common standard deviation (SD) of 1.1%, and the true difference between sotagliflozin 400 mg and glimepiride is zero, 310 patients in the sotagliflozin 400 mg and glimepiride groups will ensure that the upper bound of the 2-sided 95% confidence interval (CI) of the adjusted mean difference is below 0.3% with at least 90% power. This sample size will have 80% power to test the non-inferiority of change of HbA1c from Baseline to Week 52 in completers, with a 30% dropout rate.

A sample size of 310 patients in sotagliflozin 400 mg group and 155 patients in placebo group will have more than 99% power to detect a treatment difference of 0.6% in mean HbA1c change from Baseline to Week 26 between sotagliflozin 400 mg and placebo (SD 1.2%; 2-sided 5% significance level).

A sample size of 155 patients in sotagliflozin 200 mg group and 155 patients in placebo group will have 95% power to detect a treatment difference of 0.5% in mean HbA1c change from Baseline to Week 26 between sotagliflozin 200 mg and placebo (SD 1.2%; 2-sided 5% significance level).

The total sample size is 930 patients to be randomized (sotagliflozin 400 mg group: 310; sotagliflozin 200 mg group: 155; glimepiride: 310; placebo: 155).

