2.3.1.2 Completers population

The completers population is a subset of the ITT population who complete the 52-week Treatment Period and do not start rescue therapy. Sensitivity and subgroup analyses for the primary endpoint of change from Baseline to Week 52 HbA1c comparisons will be conducted on this population.

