Using either imputation method, missing endpoint data will be imputed 2000 times to generate multiple datasets with complete data. Other details of the imputation procedures such as the seed number and sort ordering are specified in the SAS programs. The change from baseline to Week 52 (or Week 12 for SBP) will be derived from observed and imputed HbA1c values at Week 52 (or Week 12 for SBP). Each of the complete datasets after the imputation will be analyzed using the ANCOVA model with treatment groups (sotagliflozin 400 mg, sotagliflozin 200 mg, glimepiride, and placebo groups), randomization stratum of HbA1c at Screening ($\leq 8.5\%$, $> 8.5\%$), randomization stratum of SBP at Screening (< 130 mmHg, ≥ 130 mmHg), and country as fixed factors, and baseline HbA1c value as a covariate. Results from each analysis will be combined using Rubin's formula to provide the adjusted mean change in HbA1c from Baseline to Week 52 (or Week 12 for SBP) for each treatment group, as well as the between-group differences and their associated 95% CIs. If the upper bound of the 2-sided 95% CI for the adjusted mean difference (sotagliflozin 400 mg versus glimepiride) in HbA1c change from Baseline to Week 52 is $< 0.3\%$, then non-inferiority will be declared.

Sensitivity analyses

A sensitivity analysis will be conducted with the 52-week treatment completers (ie, all patients who complete the 52-week Treatment Period and do not start rescue therapy) using the Week 52 values and the same missing data imputation method (washout imputation method) and ANCOVA model described above.

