The tipping point analysis will be performed on the ITT population and completer's population. Similarly, the tipping point analysis will be conducted for the sotagliflozin 400 mg versus glimepiride non-inferiority endpoint only if the primary efficacy endpoint analysis yields a statistically significant finding and the upper bound of the 2-sided 95% CI associated with the non-inferiority test is $< 0.3\%$.

In addition to the tipping point analyses, if the retrieved dropout imputation is applied to the primary analysis, the analysis based on the washout imputation (ie, the backup imputation method) will be presented as a sensitivity analysis.

Assessment of treatment effect by subgroup

Descriptive analyses will be performed on the primary endpoint to summarize the treatment effects across subgroups defined by the following Baseline or Screening factors:

- Race (White, Black or African American, Asian, Other) (any race groups with fewer than 5 patients may be combined with "Other" category as appropriate).
- Ethnicity (Hispanic, Not Hispanic).
- Age group (< 50 years, ≥ 50 to < 65 years, ≥ 65 years) (any category with fewer than five patients may be combined with another category as appropriate).
- Gender (Male, Female).
- Baseline BMI level ($< 30, \geq 30$ kg/m²).
- Baseline HbA1c ($\leq 8.5\%, > 8.5\%$).
- Baseline SBP (< 130 mmHg, ≥ 130 mmHg).

- Baseline eGFR (≥ 30 to < 60 mL/min/1.73 m² [Moderate decrease in GFR], ≥ 60 to < 90 mL/min/1.73 m² [Mild decrease in GFR], and ≥ 90 mL/min/1.73 m² [Normal]).
- Duration of diabetes (< 10 , ≥ 10 years).
- Country.

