- Non-inferiority comparison of sotagliflozin 200 mg and glimepiride on change from Baseline to Week 52.
- Superiority comparison of sotagliflozin 400 mg and glimepiride on change from Baseline to Week 52.

Missing data will be imputed at Week 26 or Week 52 as appropriate. The sotagliflozin groups will be penalized incrementally by a penalty, and repeated until the upper bound of the 2-sided 95% CI is $\geq 0.3\%$ for the non-inferiority comparison or until the p-value for treatment effect between the two treatment groups is >0.05 for the superiority comparison, respectively.

The tipping-point analysis will be performed only if the respective secondary endpoint comparison is statistically significant at a two-sided $\alpha = 0.05$.

A sensitivity analysis will also be conducted with the treatment completers (ie, all patients who complete the 26-week double-blind treatment period and do not start rescue therapy) for noninferiority of sotagliflozin 400 mg versus glimepiride on HbA1c reduction using the same ANCOVA model described in [Section 2.4.4.1](#). The washout imputation method will be used, where missing endpoint data in all treatment groups are imputed from a model estimated from patients in the placebo group who have the endpoint data available. The imputation model will include the randomization strata and the corresponding baseline value. Missing data will be imputed using the regression method.

Assessment of treatment effect by subgroup

Similar to that is described in [Section 2.4.4.1](#), the treatment effects for the following treatment group comparisons across subgroups will be estimated for the change from Baseline in HbA1c in the ITT population, and using the same MI method for the primary endpoint analysis:

- Sotagliflozin 400 mg group vs. placebo group at Week 26.
- Sotagliflozin 200 mg group vs. placebo group at Week 26.
- Sotagliflozin 200 mg group vs. glimepiride group at Week 52.

The ANCOVA model will include treatment groups (sotagliflozin 400 mg, sotagliflozin 200 mg, glimepiride, and placebo groups), randomization stratum of Screening HbA1c ($\leq 8.5\%$, $>8.5\%$), randomization stratum of Screening SBP (<130 mmHg, ≥ 130 mmHg), subgroup factor, treatment-by-subgroup factor, and country as fixed factors and using baseline HbA1c value as a

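### SAP 2.4.4.2 defines a completer sensitivity analysis on a 26-week double-blind period that the trial does not have; corrected to 52 weeks, it repeats the analysis already in 2.4.4.1

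*SAP*

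**What the plan says.** The sensitivity part of SAP 2.4.4.2 adds an analysis in treatment completers, defined as "all patients who complete the 26-week double-blind treatment period and do not start rescue therapy". It is to be run "for noninferiority of sotagliflozin 400 mg versus glimepiride on HbA1c reduction using the same ANCOVA model" as in 2.4.4.1, with missing endpoint values filled by washout imputation from the placebo group. The sentence gives no endpoint week.

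The other relevant places read differently:

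- SAP 1.1 describes "a 52-week double-blind and double-dummy Treatment Period". Week 26 is a scheduled HbA1c visit inside that period (Protocol 9.1.5.1), not the end of one.
- SAP 2.3.1.2 defines the only completers population: "a subset of the ITT population who complete the 52-week Treatment Period and do not start rescue therapy". It assigns that population to the primary endpoint.
- SAP 2.4.4.1 already plans a completer analysis of the primary comparison in "all patients who complete the 52-week Treatment Period and do not start rescue therapy", with Week 52 values, washout imputation and the same ANCOVA.
- Protocol 11.4.2.1 says the same of the primary endpoint: "A sensitivity analysis will be conducted with the 52-week treatment completers".
- SAP 1.3 claims "80% power to test the non-inferiority of change of HbA1c from Baseline to Week 52 in completers", allowing for 30% dropout.
- SAP Appendix D lists completers in the secondary-endpoint row, for HbA1c change to Week 52.
- SAP 2.4.4.4 contains no Week 26 comparison with glimepiride. The Week 26 tests are against placebo, and the only secondary non-inferiority test is 200 mg versus glimepiride at Week 52.

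**The concern.** The definition rests on a treatment period that does not exist in this trial, and no reading of the sentence fits the rest of the plan.

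- **Read at Week 52 as written.** The primary comparison gets two completer results from two different populations. The 2.4.4.2 set admits patients who stopped study treatment between Week 26 and Week 52. Patients off treatment tend to pull the arms together, which makes non-inferiority easier to show. A completer analysis is meant to check the result in patients who stayed on treatment.
- **Read at Week 26.** It is a supportive estimate for a contrast that appears in no objective and not in the testing sequence.
- **Read as 52-week completers at Week 52.** It is the analysis already in 2.4.4.1.

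SAP version 3 is dated 03-Apr-2020 and records database lock on 12Sep2019. Any ambiguity about the analysis set would therefore be settled with the data in hand.

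**Working it through.** **Inputs.** From SAP 1.3: 310 per arm for 400 mg and glimepiride, 155 on placebo, SD 1.1%, 30% dropout, 80% completer power. From SAP 2.4.4.1: margin 0.3%, 1-sided alpha 0.025. Assumed: when patients leave, and that those added by a 26-week rule show no difference between arms. Rescue is not counted.

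**1. The plan's own figure.** 52-week completers: 0.7 × 310 = 217 per arm. SE = 1.1 × √(2/217) = 0.1056. Power at a true difference of 0 is Φ(0.3/0.1056 − 1.96) = 81.1%. This agrees with the stated 80% and confirms that the completer power rests on Week 52.

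**2. Size of a 26-week set (n per arm).**

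| Timing of the 30% dropout | n | Added to 217 | Share not 52-week completers |
|---|---|---|---|
| All before Week 26 | 217 | 0 | 0% |
| Constant rate: 310 × √0.7 | 259.4 | 42.4 | 16% |
| All after Week 26 | 310 | 93 | 30% |

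**3. Dilution.** If 52-week completers truly differ by 0.3 and the added patients by 0, the difference in the set is d = 0.3 × 217/n: 0.300, 0.251 and 0.210.

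**4. Chance of an upper 95% bound below 0.3, all added patients observed at Week 52.** P = Φ((0.3 − d)/SE − 1.96), with SE = 1.1 × √(2/n).

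- n = 217: Φ(0 − 1.96) = 2.5%
- n = 259.4, SE 0.0966: Φ(0.049/0.0966 − 1.96) = 7.3%
- n = 310, SE 0.0884: Φ(0.090/0.0884 − 1.96) = 17.3%

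**5. Same chance, all added patients washout-imputed.** Both arms draw from the same placebo model, so the imputed patients add almost nothing to the sampling variation of the difference: SD = 0.1056 × 217/n, or 0.0883 and 0.0739. Rubin's rules still give an SE of about 0.106 and 0.103 (simulated with 217 observed per arm and 0.7 × 155 ≈ 109 placebo completers). Then P = Φ((0.3 − d − 1.96 × SE)/SD).

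- n = 259.4: Φ((0.049 − 0.2078)/0.0883) = 3.6%
- n = 310: Φ((0.090 − 0.2019)/0.0739) = 6.5%

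Direct simulation gives about 3.5% and 7%. The result shifts slightly with the assumed placebo mean.

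**6. Disagreement when the true difference is 0.** Power is 81.1% in the 52-week set and 87.4% in the 26-week set at a constant rate. The sets are nested, with correlation √(217/259.4) = 0.915. The two analyses then disagree in 9.4% of trials. In 7.9 points only the 26-week set passes; in about 1.6 points only the 52-week set does.

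**The case against.** The strongest reply is that this is a wording slip with an obvious correction. The SAP defines one completers population, at 52 weeks. The sentence points back to the ANCOVA in 2.4.4.1, whose HbA1c endpoint is Week 52, and Appendix D also gives Week 52. This largely stands. A neighbouring slip points the same way: 2.4.4.2 also treats patients without a Week 26 HbA1c as non-responders for a Week 52 responder variable. That both are carried-over text is an inference. It does not remove the need for correction, because the rule as written is wrong.

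It is also fair that a supportive estimate at Week 26 is not barred by the testing sequence, and that the rescue condition has no time limit, so patients rescued after Week 26 need not enter the set. Both points stand.

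Four stronger readings are tempting, and the documents do not support them:

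- **That the false-pass chance is 7% or 17%.** Those figures require every added patient to have an observed Week 52 value. The paragraph prescribes washout imputation for missing values, and the documents do not say how many would be missing.
- **That 9% disagreement shows bias.** At a true difference of 0 there is nothing to dilute. Most of it reflects the larger set having more power.
- **That a different comparison was meant, such as 200 mg versus glimepiride, and should now be named.** SAP 2.3.1.2 and Protocol 11.4.2.1 tie completers to the primary endpoint. "The tipping point analysis will be performed on the ITT population and completer's population" stands in the primary-endpoint section and does not extend this.
- **That the definition was loosened after lock.** The SAP's change table, part of it redacted, does not show when the sentence entered.

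**Conclusion.** The point holds as an error in a stated analysis rule. The 26-week definition contradicts the trial's 52-week period, the SAP's own completers population, the completer power statement, the protocol and Appendix D.

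The effect is limited to one supportive analysis. Followed literally at Week 52, the set gains 0 to 93 patients per arm, about 42 at a constant dropout rate. The chance of meeting the margin when completers truly differ by 0.3% rises from 2.5% to about 3.5 to 7% at a constant rate, and to about 7 to 17% if all dropout falls after Week 26. The lower end applies if all added patients are imputed, the upper if all are observed. If all dropout falls before Week 26, nothing changes. These figures are illustrative: they rest on the plan's 30% dropout, on assumed timing, and on no difference between arms in the added patients.

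The primary test, alpha, sample size and the completer analysis in 2.4.4.1 are not affected. A reader should not infer that the non-inferiority conclusion or its 52-week check is compromised.

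**What to change.** In SAP 2.4.4.2, replace the 26-week definition with the completers population of 2.3.1.2 and state Week 52 values. The paragraph is then the analysis already specified in 2.4.4.1, so delete it as a duplicate. Reconcile the completers entry in the secondary-endpoint row of Appendix D with 2.3.1.2, which limits that population to the primary endpoint.

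Do not add completer comparisons for 200 mg or for superiority. Neither 2.3.1.2 nor the protocol plans them, and choosing them after lock would be worse than the slip.

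Record the edit in the SAP history as made after the 12Sep2019 database lock.

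Cost: one paragraph, one appendix entry and one supportive table dropped. No new data.

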2.4.4.3 Analysis of other efficacy endpoints

The analysis of other endpoints (see [Section 2.1.3.3](#)) will be descriptive with no formal testing. Summary statistics at scheduled visits based on observed value will be provided by each treatment group. Graphical presentations will also be used to illustrate trends over time as appropriate.

Hospital visits due to hypoglycemia includes emergency room visit, outpatient visit and any hospitalization due to hypoglycemia. It is identified in e-CRF “Hypoglycemic Event” page as those documented as ticked “Yes” to the question “As a result of this hypoglycemia event, did a hospital visit occur?” The number (%) of patients with hospital visits due to hypoglycemia will be provided by each treatment group during the TEAE period defined for hypoglycemia, as well as the incidence rate in patient years if any patients have multiple hospital visits due to hypoglycemia. The number (%) of patients who used rescue therapy and a KM curve for the time-to-first rescue therapy will be provided by treatment group. A list of patients who used rescue therapy will also be provided (see [Section 2.5.4](#)).

For the categorical endpoints of HbA1c responders (<6.5% and <7%, respectively) and HbA1c responders with no hypoglycemic event, summary tables and graphs will be provided by each treatment group at scheduled visits. All values will be used to determine whether a patient is a responder or not at each visit, even if they are measured after IMP discontinuation or rescue medication use. Patients who have no HbA1c measurement at each scheduled visit will be treated as non-responders. For the composite endpoint of HbA1c responders and no documented symptomatic hypoglycemic event, a patient will be treated as a responder only if the criterion is met for each component.

2.4.4.4 Multiplicity issues

To control for the family-wise Type I error, a fixed-sequence testing procedure will be applied.

- The primary endpoint of the HbA1c change from Baseline to Week 52 comparing sotagliflozin 400 mg versus glimepiride will be tested at $\alpha = 0.025$ (1-sided) using a non-inferiority margin of 0.3% of HbA1c change. Once the non-inferiority is declared (the upper bound of the 2-sided 95% CI of the adjusted mean difference between sotagliflozin 400 mg and glimepiride is <0.3%), the following secondary hypothesis based on change from Baseline scores will be tested in the following prioritized order :The superiority of sotagliflozin 400 mg compared to glimepiride on:
 - Change in body weight from Baseline to Week 52,
 - Change in SBP from Baseline to Week 12 in patients with baseline SBP ≥ 130 mmHg,
 - Change in SBP from Baseline to Week 12 in all patients,

- The proportion of patients with at least one documented symptomatic hypoglycemic event (≤ 70 mg/dL) during the 52-week Treatment Period.
- The superiority of sotagliflozin 400 mg compared to placebo on the change in HbA1c from Baseline to Week 26.
- The superiority of sotagliflozin 200 mg compared to placebo on the change in HbA1c from Baseline to Week 26.
- The superiority of sotagliflozin 400 mg compared to placebo on:
 - Change in body weight from Baseline to Week 26,
 - Change in SBP from Baseline to Week 12 in patients with baseline SBP ≥ 130 mmHg,
 - Change in SBP from Baseline to Week 12 in all patients.
- The non-inferiority of sotagliflozin 200 mg compared to glimepiride on the change in HbA1c from Baseline to Week 52.
- The superiority of sotagliflozin 400 mg compared to glimepiride on the change in HbA1c from Baseline to Week 52.

If any hypothesis is found to be not statistically significant, the testing procedure will be stopped and the following hypotheses will not be tested. The non-inferiority hypothesis will be declared significant if the upper bound of the 2-sided 95% CI for the adjusted mean difference is < 0.3 . The superiority hypothesis will be declared statistically significant at $\alpha = 0.05$ (2-sided).

No multiplicity adjustment will be made on efficacy variables other than those mentioned above.

2.4.5 Analyses of safety data

The summary of safety results will be presented by treatment group.

The “observation period” defined in [Section 2.1.4](#) is applicable to all safety analyses for the classification of AEs, determination of treatment-emergent PCSA values and the last on-treatment value for the laboratory, vital sign and ECG.

General common rules

All safety analyses will be performed on the safety population as defined in [Section 2.3.2](#), unless otherwise specified, using the following common rules:

- Safety data in patients who do not belong to the safety population (eg, exposed but not randomized) will be listed separately.
- The baseline value (with the exception of serum creatinine and eGFR) is defined as the last available value before the first dose of double-blind IMP. For serum creatinine and eGFR, the baseline value is defined as the average of all values before the first dose of double-blind IMP.

- The PCSA values are defined as abnormal values considered medically important by the Sponsor according to predefined criteria/thresholds based on literature review and defined by the Sponsor for clinical laboratory tests, vital signs, and ECG ([Appendix B](#)).
- PCSA criteria will determine which patients had at least one PCSA during the TEAE period, taking into account all evaluations performed during the TEAE period, including nonscheduled or repeated evaluations. The number of all such patients will be the numerator for the on-treatment PCSA percentage.
- The treatment-emergent PCSA denominator by group for a given parameter will be based on the number of patients assessed for that given parameter in the TEAE period by treatment group on the safety population.
- For laboratory parameters cited in the protocol as efficacy endpoints (including HbA1c and plasma glucose, etc), PCSA summaries will not be provided. These parameters will be summarized in efficacy [Section 2.4.4](#). For creatinine and eGFR, PCSA summaries will be presented in safety [Section 2.4.5](#) while descriptive summaries in efficacy [Section 2.4.4](#).
- For quantitative safety parameters based on central laboratory/reading measurements, descriptive statistics will be used to summarize results and change from Baseline values by visit and treatment group. Summaries will include the last on-treatment value. The last on-treatment value is commonly defined as the value collected at the same day/time of the last administration of IMP. If this value is missing, this last on-treatment value will be the closest value prior to the last dose administration.
- The analysis of the safety variables will be essentially descriptive and no systematic testing is planned. Relative risks versus comparator (glimepiride or placebo) and their 95% CIs may be provided, if relevant.
- Selected safety analyses will be summarized by age, gender, racial subgroups, and any pertinent subgroups (see details in [Section 2.4.5.1](#) and [Section 2.4.5.2](#)).

